6.1.2.4 Pharmacodynamics Markers

- Change from baseline to Week 12 in plasma concentrations of luteinizing hormone (LH), follicle-stimulating hormone (FSH), estradiol (E2), and sex hormone-binding globulin (SHBG).

6.1.3 Exploratory Efficacy Endpoints

The exploratory endpoints include the effect of ESN364 on the following:

- **CCI** [REDACTED]
- Level of PK plasma concentrations of ESN364 and metabolite **CCI** [REDACTED] at pre-specified timepoints;
- Change in weight and waist circumference from baseline to Weeks 4, 8, 12, and 15;
- Mean change in the frequency of moderate to severe 12h day time vasomotor symptoms from baseline to Week 4;
- Mean change in the frequency of moderate to severe 12h day time vasomotor symptoms from baseline to Week 12;
- Mean change in the severity of moderate to severe 12h day time vasomotor symptoms from baseline to Week 4;
- Mean change in the severity of moderate to severe 12h day time vasomotor symptoms from baseline to Week 12;
- Mean change in the frequency of moderate to severe 12h night time from baseline to Week 4;
- Mean change in the frequency of moderate to severe 12h night time from baseline to Week 12;
- Mean change in the severity of moderate to severe 12h night time from baseline to Week 4; and
- Mean change in the severity of moderate to severe 12h night time from baseline to Week 12.

6.2 Safety Variables

Safety variables will include the following:

- Incidence and severity of treatment-emergent adverse events (TEAEs);
- Endometrial health assessment (transvaginal ultrasound ± endometrial biopsy);
- Vital signs (sitting systolic and diastolic blood pressure and pulse rate);
- Laboratory tests (hematology, biochemistry, urinalysis, and coagulation);
- 12-lead electrocardiogram (ECG) parameters;
- Plasma bone density marker concentrations;

- Physical examinations; and
- Columbia Suicide Severity Rating Scale (C-SSRS).

A TEAE is defined as an adverse event observed after starting administration of study drug through 7 days after the last dose of study drug. If the adverse event occurs on the day of the first dose and the onset time is on or after the time of the first dose of study drug or the onset time is missing, then the adverse event will be considered treatment emergent. If the adverse event occurs on the day of first dose and the onset time is before the time of the first dose of study drug, then the adverse event will not be considered treatment emergent. If a subject experiences an event both during the pre-investigational period that continues into the investigational period, the event will be considered as TEAE only if it has worsened in severity (i.e. it is reported with a new start date).

A drug-related TEAE is defined as any TEAE related to study treatment as assessed by the investigator or with missing assessment of the causal relationship.

Other safety endpoints will be considered treatment emergent if observed after starting administration of study drug through 1 day after the last dose of study drug.

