6.4 Follow-Up Visit (Week 15 [Visit 6])

The follow-up visit should occur approximately 3 weeks after the last intake of study drug. For subjects requiring a repeat biopsy, the follow-up visit will occur 4 weeks after Week 12 (Visit 5). The following procedures will be performed at the follow-up visit (Week 15 [Visit 6]):

- Review recorded vasomotor symptom frequency and severity;
- Record HFRDIS;
- Record post-baseline LSEQ;
- Record GCS;
- Record MENQoL;

- Record C-SSRS;
- Perform physical examination, including weight and waist circumference;
- Collect blood sample for:
 - Clinical laboratory tests (including biochemistry and hematology);
 - PD;
 - PGX if not collected at previous visit (can be taken at any time during the study following signed informed consent [see Section 6.1]), and
 - Bone turnover markers (including BALP, P1NP, and CTX);
- Collect urine sample for urinalysis;
- Collect vital signs, including oral/tympanic temperature, blood pressure (sitting), and pulse rate (supine after 5 minutes of rest);
- Perform triplicate 12-lead ECG (supine after 10 minutes of rest); and
- Review concomitant medications and assess adverse events.

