9.1 Adverse Events

An adverse event is defined as any untoward medical occurrence in a clinical investigation subject administered a pharmaceutical product, which does not necessarily have a causal relationship with this treatment. An adverse event can therefore be any unfavorable and/or unintended sign (including an abnormal laboratory finding), symptom, or disease temporally associated with the use of an investigational medicinal product, whether or not related to the investigational medicinal product. All adverse events, including observed or volunteered problems, complaints, or symptoms, are to be recorded on the appropriate eCRF.

Adverse events, which include clinical laboratory test variables, will be monitored and documented from the time of informed consent until study participation is complete. Subjects should be instructed to report any adverse event that they experience to the Investigator. Investigators should make an assessment for adverse events at each visit (excluding Visits 2A, 3A, and 4A) and record the event on the appropriate adverse event eCRF.

Wherever possible, a specific disease or syndrome rather than individual associated signs and symptoms should be identified by the Investigator and recorded on the eCRF. However, if an observed or reported sign or symptom is not considered a component of a specific disease or syndrome by the Investigator, it should be recorded as a separate adverse event on the eCRF. Additionally, the condition that led to a medical or surgical procedure (eg, surgery, endoscopy, tooth extraction, or transfusion) should be recorded as an adverse event, not the procedure.

Any medical condition already present at the screening visit will be recorded as medical history and should not be reported as an adverse event. Any medical condition or signs or symptoms present at screening that change in severity or seriousness at any time during the study should be reported as an adverse event.

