9.3 Serious Adverse Event Reporting – Procedures for Investigators

Initial Reports

All SAEs occurring from the time of informed consent (see Section 9.1) until 30 days following the last administration of study drug must be reported to Medpace Clinical Safety within 24 hours of the knowledge of the occurrence (this refers to any adverse event that meets any of the aforementioned serious criteria). All SAEs that the Investigator considers related to study drug occurring after the 30-day follow-up period must be reported to the Sponsor.

To report the SAE, complete the SAE form electronically in the electronic data capture (EDC) system for the study. When the form is completed, Medpace Safety personnel will be notified electronically and will retrieve the form. If the event meets serious criteria and it is not possible to access the EDC system, send an email to Medpace Safety at [contact] or call the Medpace SAE hotline (phone number listed below), and fax the completed paper SAE form to Medpace (fax number listed below) within 24 hours of awareness. When the EDC system becomes available, the SAE information must be entered within 24 hours of the system becoming available.

Safety Contact Information: Medpace Clinical Safety

Medpace SAE hotline – USA:

[contact], dial 3 or [contact], dial 3

[contact] or [contact]

E-mail: [contact]

Follow-Up Reports

The Investigator must continue to follow the subject until the SAE has subsided or until the condition becomes chronic in nature, stabilizes (in the case of persistent impairment), or the subject dies.

Within 24 hours of receipt of follow-up information, the Investigator must update the SAE form electronically in the EDC system for the study and submit any supporting documentation (eg, redacted subject discharge summary or autopsy reports) to Medpace Clinical Safety via fax or e-mail. If it is not possible to access the EDC system, refer to the procedures outlined above for initial reporting of SAEs.

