9.14.2 Suspected Drug-Induced Liver Injury

Subjects will be monitored for DILI from randomization to 21 days following the last administration of study drug (refer to Appendix D for detailed procedures). Subjects must be immediately withdrawn from the study and follow the evaluation for suspected DILI in Appendix D, if they meet any of the following criteria:

- ALT or AST $>8 \times$ ULN;
- ALT or AST $>5 \times$ ULN for more than 2 weeks;
- ALT or AST $>3 \times$ ULN **AND** total bilirubin $>2 \times$ ULN or INR $>1.5 \times$ ULN; or
- ALT or AST $>3 \times$ ULN with the appearance of fatigue, nausea, vomiting, right upper quadrant pain or tenderness, fever, rash, and/or eosinophilia ($>5\%$).

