7.5.1 Adverse Events

Summaries and listings of SAEs and Serious TEAEs include SAEs upgraded by the sponsor based on review of the Sponsor's list of Always Serious terms if any upgrade was done.

The coding dictionary for this study will be MedDRA. It will be used to summarize AEs by SOC and PT.

An overview table will include the following details:

- Number of TEAEs,
- Number and percentage of subjects with TEAEs,
- Number of drug related TEAEs,
- Number and percentage of subjects with causally drug related TEAEs,
- Number of serious TEAEs,
- Number and percentage of subjects with serious TEAEs,
- Number of serious drug related TEAEs,
- Number and percentage of subjects with serious drug related TEAEs,
- Number of TEAEs leading to permanent discontinuation of study drug,
- Number and percentage of subjects with TEAEs leading to permanent discontinuation of study drug,
- Number and percentage of subjects with TEAEs leading to study drug interruption, and
- Number of deaths.

The number and percentage of subjects with TEAEs, as classified by SOC and PT will be summarized for each treatment group. Summaries will be provided for:

- TEAEs,
- drug related TEAEs,
- serious TEAEs,
- drug related serious TEAEs,

- TEAEs leading to permanent discontinuation of study drug,
- drug related TEAEs leading to permanent discontinuation of study drug,
- TEAEs excluding serious adverse events that equal to or exceed a threshold of 5% in any treatment group, and
- common TEAEs that equal to or exceed a threshold of 5% in any treatment group.

The number and percentage of subjects with TEAEs, as classified by PT only, will be summarized for each treatment group.

The number of TEAEs and the number and percentage of subjects with TEAEs, as classified by SOC and PT will also be summarized by severity and by relationship to study drug. In the subject count, if a subject has multiple TEAEs with the same SOC or PT, but with differing severity or relationship, then the subject will be counted only once with the worst severity and highest degree of relationship, however, if any of the severity or relationship values are missing then the subject will be counted only once with missing severity or relationship. In the adverse event count, the adverse events will be presented in each category they were classified to. Drug related TEAEs will be presented in a similar way by severity only.

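### Adverse events starting more than 7 days after the last dose, unless fatal or of special interest, have no itemised SOC/PT table by treatment group

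*SAP*

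**What the plan says.** **The analysis window.** SAP 6.2 defines a TEAE as "an adverse event observed after starting administration of study drug through 7 days after the last dose of study drug". TEAE incidence and severity is the only adverse event variable in that section's list of safety variables. SAP 7.5 exempts adverse events from the one-day post-dose cut-off used for other safety data, so the 7-day definition governs them.

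**The tables.** SAP 7.5.1 states: "The number and percentage of subjects with TEAEs, as classified by SOC and PT will be summarized for each treatment group". The variants that follow (drug-related, serious, leading to discontinuation, common, by severity, by relationship) are all defined on TEAEs. In the overview table, the count of deaths is the only line without that limit. The summary of adverse events of special interest (AESIs) states no window. The opening sentence of SAP 7.5.1 names summaries of SAEs alongside those of serious TEAEs, but no all-SAE table is then itemised.

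**The collection periods.**
- Under Protocol 9.1, adverse events "will be monitored and documented from the time of informed consent until study participation is complete".
- Protocol 6.4 puts the final visit about 3 weeks after the last intake, or 4 weeks after Week 12 if a biopsy is repeated. Protocol 4.4 asks withdrawn subjects to return about 3 weeks after their last intake.
- Under Protocol 9.3, SAEs "until 30 days following the last administration of study drug must be reported to Medpace Clinical Safety".
- Protocol 9.14.2 states: "Subjects will be monitored for DILI from randomization to 21 days following the last administration of study drug".

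**The concern.** Protocol 10.2.2 says that safety will be assessed by the incidence of adverse events. In a trial with seven active arms, meant to help choose a dose for Phase 3, that means incidence by arm. The sites collect events for about three weeks off drug, and SAEs for thirty days, but the itemised incidence tables stop at day 7. An ordinary adverse event on day 12, or a non-fatal SAE on day 18, is recorded and can appear in a listing, yet enters no itemised SOC/PT comparison with placebo.

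Three kinds of record are the most exposed:
- **Clinical liver events** recorded as an AE or SAE during the protocol's own 21-day monitoring period.
- **Off-drug effects**, including those in subjects who stopped treatment early.
- **Endometrial findings** recorded as adverse events. SAP 7.5.6 only lists ultrasound and biopsy results, hyperplasia is not an AESI, and the SAP has no rule for dating a biopsy finding. Protocol 9.18 calls for central reading and, for hyperplasia, two further pathologists. A finding sampled at Week 12 but dated to its reading could therefore slip past day 7.

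**Working it through.** **Step 1. Reproduce the follow-up length.** SAP 7.10.6 sets the target days at D85 for Visit 5 and D106 for Visit 6.
- 106 − 85 = 21 days, which matches the protocol's figure of about 3 weeks.
- If the last dose is on D84, 106 − 84 = 22 days. I use 21.

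**Step 2. Compare each collection period with the 7-day window.** Days outside = end of collection − 7; share outside = days outside / end of collection.

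| Record | Collected to (days after last dose) | Days outside | Share outside |
|---|---|---|---|
| AEs, usual final visit | 21 | 21 − 7 = 14 (days 8–21) | 14/21 = 67% |
| AEs, repeat-biopsy subjects | 28 | 28 − 7 = 21 (days 8–28) | 21/28 = 75% |
| SAEs | 30 | 30 − 7 = 23 (days 8–30) | 23/30 = 77% |

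The 28-day row takes the last dose to be at Week 12. The 30-day limit is stated in the protocol. The 21-day limit for AEs is inferred from the visit schedule; the only literal 21-day figure is the one for DILI monitoring. These shares are of calendar days, not of events.

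**Step 3. Ask which late events have another by-arm output.**
- Deaths: yes, in the overview count.
- AESIs (uterine bleeding, oral/facial paresthesia, ALT or AST above 3 × ULN): possibly, since no window is stated.
- Liver laboratory criteria: yes. SAP 7.5.2.1 tabulates them by arm for the treatment and follow-up periods.
- SAEs: unclear, since summaries are mentioned but none is specified.
- All other adverse events: none itemised.

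**Step 4. Scale, by assumption only.** The documents give no rate of events starting after day 7. Let p be the assumed share of subjects with a first such event. With 44 subjects per arm and 352 in all, the expected number per arm is 44p, the expected total is 352p, and the chance of at least one in a given arm is 1 − (1 − p)^44.

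| p | Per arm | Total | At least one in an arm |
|---|---|---|---|
| 1% | 0.4 | 3.5 | 36% |
| 2% | 0.9 | 7.0 | 59% |
| 5% | 2.2 | 17.6 | 90% |
| 10% | 4.4 | 35.2 | 99% |

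This shows the order of size if such events occur. It does not estimate how many will.

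**The case against.** The strongest reply is that collecting, reporting and tabulating are separate functions. The protocol defines no TEAE window, so a reader who infers that the SAP contradicts the protocol goes too far. Nor do the documents show that 7 days is too short: no half-life is visible, and part of the clinical background is redacted. A short window keeps off-drug background events out of the main tables, which is a legitimate aim. This stands, although the SAP gives no reason for choosing 7 days.

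Three other strong readings are tempting but not supported.

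- **That delayed liver injury could not be compared between arms.** SAP 7.5.2.1 tabulates the enzyme and bilirubin criteria by arm through follow-up and adds a listing of suspected DILI. (The same section also refers to the highest value in the treatment period; that is a separate matter of wording.) ALT or AST elevation is also an AESI. Only clinical AE and SAE records are affected.
- **That hyperplasia first found at a repeat biopsy would be lost.** Protocol 6.3.7 and 9.18 allow a repeat only after an abnormal Week 12 biopsy, and then only if clinically indicated. The abnormality is normally sampled at the end of treatment, inside the window. What remains is the missing dating rule.
- **That two thirds or three quarters of late events are dropped.** The percentages count days, and the SAE figure includes days 22–30, after the usual final visit.

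The SAE wording in SAP 7.5.1 may mean that a wider SAE table is intended. As written, that is an ambiguity to settle.

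**Conclusion.** The point holds as a reporting gap. Non-fatal, non-AESI adverse events that start more than 7 days after the last dose have no itemised SOC/PT table by arm, although the protocol collects them. The windows for the SAE and AESI summaries are unstated. The gap spans 14 of 21 post-dose days for adverse events (taking the final visit at 21 days) and 23 of 30 for SAEs. How many events it affects is unknown. It does not make the 7-day window wrong, and it leaves the deaths count and the liver laboratory table as they are. The change is worth making before unblinding because it is cheap and improves the safety comparison between doses and placebo.

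**What to change.** Keep the 7-day TEAE tables. In SAP 7.5.1:

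1. Add by-arm SOC/PT tables of all adverse events with onset from first dose through the final follow-up visit, and of all SAEs through 30 days after the last dose. The SAE table also settles what the opening sentence of that section refers to.
2. State that the AESI summary uses the same full follow-up window.
3. State that an endometrial biopsy finding recorded as an adverse event is dated to the biopsy at which it was first sampled, not to the reading date.

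The cost is SAP wording and one more set of tables from data already collected, with no change to study conduct or sample size. The downside is that the added tables will include some off-drug background events. Keeping them apart from the TEAE tables lets the reader see both.

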9.1.3 Assessment of Adverse Events by the Investigator

The Investigator will assess the severity (intensity) of each adverse event as mild, moderate, or severe, and will also categorize each adverse event as to its potential relationship to study drug using the categories of yes or no.

Assessment of Severity:

Mild – An event that is easily tolerated and generally not interfering with normal daily activities.

Moderate – An event that is sufficiently discomforting to interfere with normal daily activities.

Severe – An event that is incapacitating with inability to work or perform normal daily activities.

Causality Assessment:

The relationship of an adverse event to the administration of the study drug is to be assessed according to the following definitions:

No (unrelated, not related, no relation) – The time course between the administration of study drug and the occurrence or worsening of the adverse event rules out a causal relationship and another cause (concomitant drugs, therapies, complications, etc.) is suspected.

Yes (related) – The time course between the administration of study drug and the occurrence or worsening of the adverse event is consistent with a causal relationship and no other cause (concomitant drugs, therapies, complications, etc.) can be identified.

The definition implies a reasonable possibility of a causal relationship between the event and the study drug. This means that there are facts (evidence) or arguments to suggest a causal relationship.

The following factors should also be considered:

- The temporal sequence from study drug administration-
 - The event should occur after the study drug is given. The length of time from study drug exposure to event should be evaluated in the clinical context of the event.
- Underlying, concomitant, intercurrent diseases-
 - Each report should be evaluated in the context of the natural history and course of the disease being treated and any other disease the subject may have.
- Concomitant drug-
 - The other drugs the subject is taking or the treatment the subject receives should be examined to determine whether any of them might be recognized to cause the event in question.

- Known response pattern for this class of study drug-
 - Clinical and/or nonclinical data may indicate whether a particular response is likely to be a class effect.
- Exposure to physical and/or mental stresses-

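### SAP 6.2: an adverse event that starts between the screening visit and the first dose, then becomes serious on treatment with its severity grade unchanged, is not treatment-emergent as worded and is missing from the itemised serious-TEAE rows

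*SAP*

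**What the plan says.** SAP 6.2 gives a general definition: "A TEAE is defined as an adverse event observed after starting administration of study drug through 7 days after the last dose of study drug". It then adds a specific rule for an event that begins in the pre-treatment period and carries over into treatment: "the event will be considered as TEAE only if it has worsened in severity (i.e. it is reported with a new start date".

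Protocol 9.1 has adverse events collected early: they "will be monitored and documented from the time of informed consent until study participation is complete". On conditions the woman already has, it says "Any medical condition already present at the screening visit will be recorded as medical history and should not be reported as an adverse event". It adds that medical conditions, signs or symptoms "present at screening that change in severity or seriousness at any time during the study should be reported as an adverse event".

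Protocol 9.1.3 says the investigator "will assess the severity (intensity) of each adverse event as mild, moderate, or severe". Protocol 9.2 defines seriousness separately, by outcome: death, threat to life, hospital admission, disability, congenital anomaly or an important medical event.

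The overview table in SAP 7.5.1 lists "Number and percentage of subjects with serious TEAEs", with a parallel row for drug-related serious TEAEs. The tables by system organ class and preferred term are restricted to TEAEs in the same way.

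**The concern.** A carried-over event has one stated way to become treatment-emergent: a rise in severity grade. A moderate event that leads to hospital admission after dosing need not change grade, because the grade describes interference with daily activity and seriousness describes the outcome. An event already graded severe has no higher grade to reach, whatever happens next.

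At stake is the by-arm comparison of serious events on treatment. The itemised serious rows count TEAEs only, so an event of this kind would be absent from the tables in which arms are compared, although the change to serious happened on study drug. Arms are small, so a single event is visible in an arm's percentage.

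**Working it through.** The plan gives no figure to reproduce. The check sets the texts side by side and takes the possible cases in turn.

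**Inputs**
- Pre-dose window: from consent at the screening visit to the first dose, at least 7 and up to 35 days (Protocol 6.2 and 9.1).
- Trigger for a carried-over event: worsened severity only (SAP 6.2).
- Severity: three levels, severe the highest (Protocol 9.1.3).
- Seriousness: a separate classification by outcome (Protocol 9.2).
- Itemised serious rows: TEAEs only (SAP 7.5.1).
- Arm size: 352/8 = 44 (SAP 4).

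**Cases**

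| Event | After the first dose | Result under SAP 6.2 |
|---|---|---|
| A. Onset between screening visit and first dose, mild or moderate | Grade rises, with or without becoming serious | TEAE; counted |
| B. Same onset, mild or moderate | Becomes serious, grade unchanged | Not a TEAE as worded; absent from the serious-TEAE rows unless a new record is opened |
| C. Same onset, already severe | Becomes serious | As B; no higher grade exists |
| D. Same onset, already severe | Stays non-serious | Not a TEAE, but never belonged in the serious rows |
| E. Present at the screening visit (medical history) | Becomes serious | Reported as an adverse event under Protocol 9.1; the record would normally start on treatment and so meet the general definition |

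The gap is cases B and C.

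**Does the new start date close it?** In SAP 6.2 the new start date is introduced by i.e., so it restates worsened severity and is not a second route. If a programmer nevertheless keys on the start date, the result depends on whether the site opened a new record. Protocol 9.1 and 9.3 give no instruction on that for an ongoing adverse event that becomes serious, so two sites could record the same course differently.

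**Scale.** One woman in one arm: 1/44 = 0.0227, or 2.3 percentage points.

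**Illustration on assumed rates.** The documents give none of these. Suppose 10% to 25% of the 352 women have an adverse event ongoing at Day 1: 352 × 0.10 = 35 to 352 × 0.25 = 88. Suppose 0.5% to 1% of those become serious on study: 35.2 × 0.005 = 0.2 to 88 × 0.01 = 0.9 events in the whole trial. This takes one event per woman and does not remove case A, which the SAP already counts. Under these assumptions it is therefore on the high side.

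**The case against.** The strongest reply is that the protocol already handles this. It tells sites that conditions "signs or symptoms present at screening that change in severity or seriousness at any time during the study should be reported as an adverse event". That stands for case E, so a reader who infers that every event beginning before the first dose is lost when it turns serious goes too far. It does not clearly reach adverse events that start after the screening visit. If *at screening* were read as the whole screening period, the gap would shrink, but the preceding sentence of Protocol 9.1 speaks of the screening visit.

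A reader might also infer that the SAP contradicts the protocol. The documents do not support that. The Protocol 9.1 sentence is a reporting rule, not a definition of treatment emergence. The SAP test is narrower, and SAP 8 does not list it as a change, but the two serve different purposes.

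A third tempting reading is that events already graded severe drop out of the serious tables. Severe is not serious; only case C is affected. It should be uncommon, since women must be in good general health and eligibility is reviewed again on Day 1.

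Nor are these events hidden. SAEs are reported from consent (Protocol 9.3), SAP 7.5.1 mentions SAE summaries and listings as well as serious TEAEs, and the count of deaths is not limited to TEAEs as worded. It remains true that no by-arm table of all SAEs is itemised.

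Finally, the recording convention may sit in eCRF or data-entry instructions that are not among these documents. That is fair, and it is why the loss is conditional on no new record being opened. It does not repair the SAP wording.

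**Conclusion.** The point holds in a narrow form. As worded, SAP 6.2 leaves out an adverse event with onset between the screening visit and the first dose that becomes serious on treatment without a change of grade, including one already severe. Unless a new record happens to be opened, it is missing from the itemised serious-TEAE and drug-related serious-TEAE rows.

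The number affected cannot be derived from the documents. On the assumed rates shown it is below one expected event in the trial, so probably zero or one; one would be 2.3 percentage points of an arm.

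A reader might infer that the serious-event tables can only be too low overall. That is true of this clause taken alone. Other SAP rules push counts upward: events on the day of first dose with no onset time are treated as emergent, missing causality counts as drug-related, and sponsor upgrades to serious are included. The documents support a small wording correction, not a finding of biased safety reporting.

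**What to change.** In SAP 6.2, state that an event starting before the first dose and continuing on treatment is a TEAE if, after the first dose and within the TEAE window, it worsened in severity **or** became serious. Identify the change by a new start date or by the date the event became serious. Say explicitly that an event already graded severe qualifies through the second route.

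Before adopting this, confirm that the date of becoming serious is captured; the documents do not show the fields of the SAE form. An alternative is to keep the definition and itemise a by-arm table of all SAEs that became serious after the first dose.

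The cost is one sentence and one programming condition, settled before unblinding. The serious-TEAE count may rise slightly. The change does not bring in a non-serious pre-dose event of unchanged grade that leads to stopping study drug, and it is not meant to.
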